1. BACKGROUND AND SIGNIFICANCE

1.1 Overview

Approaches and experiences of ongoing early adopter programs for incorporating genomic information in clinical care have to date been largely limited to examples conducted at a small group of academic institutions in few highly-specialized areas, including pharmacogenetics (1, 2), tumor-based screening (3, 4), family history-based decision support (5, 6), and diagnostic whole exome/genome sequencing (4, 7). However, studies that develop robust systems to consent, screen, return results, and that evaluate processes and outcomes of incorporating genomic risk information in clinical care for common chronic diseases are missing and urgently

needed. We propose that hypertension-attributable chronic kidney disease has emerged as a highly-relevant opportunity for a ‘prototype’ genomic medicine demonstration project that addresses common chronic illnesses managed in primary care settings. Hypertension-attributable chronic kidney disease (CKD) is characterized by

- high prevalence affecting millions of Americans (8),
- high burden of morbidity and mortality related mainly to increased cardiovascular disease risk and kidney failure or end stage renal disease (8),
- progression to kidney failure that can be modified by appropriate pharmacological interventions (9-11),
- a disproportionate burden for African Ancestry and major health disparity (12) (13-16) (17) (18),
- a substantial and testable population selective genomic risk that explains most of the excess burden of hypertension-attributable CKD risk in African Ancestry populations (19) (20) (21) (22).

Synthesis of evidence and formulation of study rationale

Synthesis: Chronic Kidney Disease (CKD), Hypertension and Blood Pressure Control. CKD is a common, complex disease affecting 26 million Americans adults (8). CKD is most commonly attributable to diabetes (40% of CKD cases) and hypertension (28% of cases). African Ancestry populations with hypertension (HTN) have 2- to 3-fold higher risk of developing CKD, and a 5-fold increased risk to progress to end stage renal disease (ESRD) when compared with whites. HTN is an established risk factor for progression of CKD and for increased cardiovascular risk with CKD. Thus targeting blood pressure control as a modifiable risk factor may both reduce CVD in people with CKD and reduce progression of CKD to end stage disease (9-11).

Synthesis: Poor adherence with renal care practice guidelines puts participants at risk for kidney failure

Importantly, major goals of practice guidelines for renal care in hypertensive participants remain unmet in clinical practice today: among Medicare participants with hypertension without diabetes, only 1 in 25 receives recommended simple lab tests (creatinine and urine albumin) to evaluate CKD, and less than half of all participants with moderate to advanced stages of CKD in the Kidney Early Evaluation Program (KEEP) are aware that they are affected (23). Among younger participants of African Ancestry CKD awareness is particularly low (23) and progression to kidney failure is typically accelerated resulting in excessive rates of ESRD (13) (18).

Improved CKD awareness and access to primary care or nephrology referral for individuals with or at risk of CKD are considered critical to improve CKD-related outcomes (24, 25). Factors associated with progression of CKD and with increased cardiovascular risk are overlapping to a large extent, including hypertension. There is strong evidence that blockade of the renin-angiotensin system is a blood pressure lowering strategy which is more effective in reducing risk of kidney and cardiovascular disease in the presence of albuminuria, a marker of CKD (26). Thus, in order to improved renal care and reduce risk for kidney failure in this population at excess risk, we urgently need new strategies:

- to improve comprehension of CKD risk and CKD awareness among participants with CKD or at risk for CKD and among their providers, and
- to increase adherence with practice guidelines targeting those risk factors that are modifiable may both reduce cardiovascular disease in people with CKD and reduce progression of CKD to end stage kidney disease.

Synthesis: APOL1 G1 and G2 risk alleles and non-diabetic kidney diseases.

A locus containing the myosin heavy chain 9 (MYH9) gene for non-diabetic kidney disease in African ancestry individuals was initially identified by admixture mapping (27, 28). Recently, three non-synonymous coding

variants in the neighboring *APOL1* gene defined two allele, termed G1 and G2 with stronger effect on non-diabetic kidney disease than MYH9 variants (19). The authors suggested that G1 and G2 alleles are exceedingly rare in non-African ancestry genomes, but in African ancestry genomes, 22.5% and 14.6% of chromosomes carry the mutually-exclusive G1 and G2 risk alleles because they were selected for by providing protection against Trypanosomiasis (sleeping sickness) in West Africa (19).

APOL1-associated kidney disease risk is best explained using a recessive model, and approximately 13% of African Americans are estimated homozygous for G1 / G2 risk alleles, suggesting that more than 3 million AA are at markedly increased risk for non-diabetic CKD (20). In our IPM Biobank, 15% of more than 5,000 AA participants were found to carry [2] risk alleles, and the odds for hypertensive CKD in this cohort were 2.7. We recently analyzed the effect of APOL risk alleles on severity of hypertension-attributed kidney disease in the African American Study of Kidney Disease and Hypertension (AASK) cohort (Table 1). *APOL1* risk alleles are highly significantly associated with CKD attributed to essential hypertension in non-diabetic AASK participants, and the odds for advanced kidney disease (significant proteinuria or serum creatinine >3 mg/dl) were >4 -fold in carriers of [2] risk alleles compared to [0,1] risk alleles (22). Heterozygous G1 or G2 risk allele status does not appear to increase kidney disease risk.

Table 1. Logistic regression model of the effect of APOL1 risk alleles on clinical phenotype AASK cases and controls

Note: creatinine >2 or >3 mg/dL approximate CKD Stage 3 or higher; ESKD indicates end stage kidney disease, i.e. CKD stage 5; urine PCR (protein creatinine ratio) > 0.22 g/g or > 0.60 g/g correlate approximately with albumin creatinine ratio (ACR) of > 30 mg/g and > 300 mg/g.

In summary, [2] *APOL1* G1 / G2 homozygous risk allele status

- explains practically all of the substantial excess genetic risk for non-diabetic CKD in African ancestry populations,
- is present in 1 out of 7 African American participants genotyped at Mount Sinai,
- is strongly and consistently associated with hypertension-attributable CKD (odds >2.7)
- is strongly and consistently associated with progressive and proteinuric states of hypertension-attributable CKD (odds >4.0) or with hypertensive ESRD (odds 7.3).

Thus, published evidence and our own Mount Sinai results strongly support our hypothesis that carriers of [2] *APOL1* risk alleles have an increased genomic risk for hypertension-attributable CKD and its progression to kidney failure.

1.2 Study Aims

GUARDD is multifaceted and has elements that involve qualitative research for a formative study to better information development of the randomized trial. This protocol is focused on the randomized controlled trial.

AIM II. Develop systems and evidence-based advice messages to enable point of care Clinical Decision Support (CDS) for primary care providers advising renal care practice guidelines with or without genomic *APOL1* risk information

Rationale. One of the highly anticipated quality improvement advantages offered by EHRs and ‘meaningful use’ is the potential for point of care Clinical Decision Support (CDS). CDS provides clinicians or participants with knowledge presented at appropriate times to improve healthcare. In this context, CDS also has the potential to increase the awareness of and adherence to, standard of care processes. Mount Sinai’s IPM conducts several early adopter projects testing utility and adoption of pharmacogenomic CDS for clinicians in real-time at the point of care. We will develop new functionality for our existing CLIPMERGE Risk Assessment Engine database (CRAE database) to deliver CDS for renal care practice guidelines based on conventional kidney disease risk assessment with or without *APOL1* genomic kidney disease risk information. Importantly, we will for the first time develop interfaces that will allow CRAE to disseminate standardized CDS to independent Epic EHR implementations across different primary care practice settings at IFH and MSMC.

Sub-Aim 2.1. Modification of CLIPMERGE Risk Assessment Engine (CRAE) technology for multiple EHR (IFH and MSMC) and renal care CDS capabilities. CRAE houses phenotypic and gene variant data necessary for the evaluating enrolled participants’ data relevant to the guidelines to be implemented for this study. The CRAE database will be populated only for enrolled participants. The CRAE database itself houses very strictly de-identified data (only). A separate function named the Broker handles all necessary translation between identified data (as needed for participant enrollment, for transactions flowing from and to Epic, and for receipt of genomic results from the CLIA lab) and de-identified data.

The CLIPMERGE-EPIC Integration. The CLIPMERGE database will include longitudinal clinical data extracted from Mount Sinai’s and IFH’s Epic EHR systems, for all consented participants enrolled in the research study; including CLIA-grade *APOL1* genotype and G1 G2 risk allele data from those that have been genotyped. Our CLIPMERGE Risk Assessment Engine (CRAE) includes this database and a rules engine that relates genome-based advice messages (renal care advice messages incorporating *APOL1* genomic risk information with conventional risk data) or conventional risk based advice messages to standard of care clinical decision support messages. During the first six months of year 1, the CLIPMERGE and Epic team at Mount Sinai will work with the Epic team at IFH to build HL7 interfaces customized between CRAE and the specific Epic version installed for IFH sites.

Reference and educational material. Upon presentation of a BPA, providers will have the opportunity to directly access reference content that further describes the evidence base for the CDS through a clickable link in the Epic SmartSet.

Sub-Aim 2.2. Development and usability testing of a library of evidence-based renal care advice messages customized for assessment of risk with and without *APOL1* G1 G2 risk allele information, and for adherence to practice guidelines for renal care in non-diabetic African ancestry participants with hypertension

Rationale. CKD awareness among participants and providers, appropriate use of tests for biochemical markers of CKD (creatinine and urinary albumin excretion) to screen for presence of CKD in those at risk, and appropriate use of pharmacological and life style interventions in those at risk for CKD progression are considered critical to improve CKD-related outcomes (ESRD, CVD, and mortality [\(24, 25\)](#)). As summarized in the paragraph “**Synthesis: Poor adherence with renal care practice guidelines puts participants at risk for kidney failure**” at the beginning of the APPROACH section, major goals of practice guidelines for renal care in hypertensive participants remain unmet in clinical practice today. Blacks have higher prevalence of hypertension (41% vs. 28%), younger age of onset, and poorer control of hypertension than Whites [\(17\)](#). Blacks also have, a 2-3x the risk for developing CKD [\(12\)](#), and the adjusted prevalence rate for ESRD is 4.1-fold higher in AA when compared with Whites [\(14-16\)](#). The differences in CKD are most pronounced among those with hypertension. Thus, it is imperative to uncover new strategies to screen and engage AAs with hypertension into programs to improve BP control and participant outcomes.

The Kidney Disease Improvement Global Outcomes (KDIGO) evidence-based practice guidelines advise the appropriate use of tests for biochemical markers of CKD (creatinine and urinary albumin excretion) to screen for presence of CKD in those at risk, and appropriate use of pharmacological and lifestyle interventions in those at risk for CKD progression are considered critical to improve CKD-related outcomes (ESRD, CVD, and mortality [\(24, 25\)](#)). Practice guidelines, including the Joint National Commission 7 (JNC7) guidelines, recommend specific medications (ACE inhibitors and ARBs) as preferred first line agents and more intensive blood pressure goal in participants with hypertensive CKD [\(9-11\)](#).

Several reports demonstrate that *APOL1* risk alleles are highly significantly associated with CKD attributed to essential hypertension in non-diabetic AASK participants, and the genetic association was most robust in individuals with progressive renal functional decline [\(22\)](#) (see our AASK Cohort data in Table 1). Because of the overwhelming strengths of the evidence, we propose to establish *APOL1* genomic risk status in non-diabetic AA participants and to incorporate the *APOL1* G1/G2 risk allele status in a recessive model together with conventional risk factors in CKD and CKD progression advice messages.

Aim III. Conduct a randomized trial assigning eligible participants to immediate genetic testing or delayed genetic testing arms in a seven (immediate testing) -to- one (delayed testing) ratio.

Sub-Aim 3.1: To examine whether increase in practice guideline-appropriate renal laboratory test ordering (renal care endpoint) will be achieved in *APOL1*-positive group vs *APOL1*-negative group.

Sub-Aim 3.2. To examine whether systolic blood pressure will decline more in the *APOL1*-positive group compared with *APOL1*-negative group.

2. ENDPOINTS

2.1 Primary Endpoints

The study has two primary endpoints, comparing patients who are *APOL1* positive (high risk) and *APOL1* negative at three months after enrollment. One primary aim is a renal care endpoint, the correct utilization, by clinicians, of urine albumin tests. The other primary aim is reduction of systolic blood pressure.

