3.4 Sample Size

The total number of people expected to participate is 2,050. Of the 1800 intervention participants, approximately 250 will test positive. We will thus have approximately 250 high risk, 250 control, and 1550 normal risk participants. The sample size for the study was calculated assuming a 10% improvement in practice guideline-appropriate renal function test ordering in the *APOL1*-positive group (40% estimated) vs. *APOL1*-negative group (30% estimated) to yield 87% power to detect the difference of interest using a two-sided chi-square test. Specifically, this includes measurement of serum creatinine and urine microalbumin. The blood pressure sub-aim, 5mmHg improvement in systolic blood pressure at 3-month follow up in *APOL1*-positive compared with *APOL1*-negative group, can be detected with 95% power.

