6.3 Follow-Up Assessments

All participants will be advised that they will be contacted to complete a follow-up study visit at 3 months and 12 months after enrollment (duration of the observation period). During follow-up visits, Study Coordinators will follow study protocol (outlined in the MOP) to conduct surveys, measure blood pressure, and obtain participant weight in order to calculate body mass index. They will enter this data directly into REDCap using tablets/laptops. The follow-up visits will take approximately 45 minutes to complete. Participants will receive a \$40 gift card for each follow-up visit completed.

Follow-up visits will be completed between 14 days prior and one month after the projected follow-up date (projected 3 month study visit due date = 3 months from date of baseline visit completion; projected 12 month study visit due date = 12 months from date of baseline visit completion). Whenever possible, participants will meet with the same Study Coordinator for follow-up visits to maintain continuity.

If the participant has a blood pressure reading greater than 190/110 during any follow up visit, study staff must complete an Elevated Blood Pressure Note, inform the participant that they have very high blood pressure and strongly advise that they get urgent and appropriate evaluation and care from a healthcare provider. Study staff must also inform study PIs.

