6.6 Return of Genetic Results

Result reporting will occur approximately 1-4 weeks after the samples are obtained (see Fig. 1 Study flow chart). The laboratory will notify the study Program Manager of when results are ready to be returned. The Program Manager will in turn alert Study Coordinators. Return of results will be done by their assigned Study Coordinators. Study Coordinators will be trained by [name], Director of Mount Sinai Genetic Counseling Program, to return risk assessment results and recommendations. They will use a Return of Results Script for this visit. *APOL1* negative participants will have their tests results returned by phone (participants in the formative study said they did not want to come back in person for a negative results) and those that are *APOL1* positive will be scheduled for an in person return of results visit. If an in person return of results visit is not able to be scheduled for an *APOL1* positive participant, we will offer the participant the opportunity to receive their results over the phone. During return of results, the Study Coordinator will disclose the genetic test result, provide simple, clear information and use "speak back" or "teach back" technique to maximize participants' comprehension of their result. In addition to verbal ROR, participants will also receive lay explanations of their test results in writing and the educational booklet about *APOL1*, blood pressure and kidney

disease. *APOL1* positive participants will review the informational booklet at the time of their return of results, *APOL1* negative participants will receive their written test results and informational booklet in the mail.

If we are unable to return an *APOL1* positive test result to the participant for at least 3 months we will notify their primary care provider so that the result can be noted in their electronic health record and the participant can be notified of their results when they get in contact with their provider, even if that is after the study has ended.

All participants will be given the option to speak to a genetic counselor after their return of results in person or by telephone, at no charge. If a participant chooses to speak with a genetic counselor, the Study Coordinator will contact the genetic counselor on behalf of the participant, and the genetic counselor will then follow-up directly with the participants.

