Once a result is returned to the participant, the Study Coordinator completes the corresponding fields in Redcap that prompts CLIPMERGE to fire a Best Practice Alert (BPA) in the participant's electronic health record the next time a primary care provider opens it. The BPA will pop up once per unique provider. A provider can choose to open the BPA and has the option of clicking on and viewing and printing information for the participant and information for him/herself. In addition to the BPA, the lab will also place a copy of the *APOL1* genetic test results in the participant's electronic medical record. Electronic Health Record Data Extraction

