6.7 Electronic Health Record Data Extraction

Electronic health data relevant to the study endpoints will be pulled for the period of 12 months prior to randomization and 12 months after randomization for all enrolled participants.

Figure 2. *APOL1* positive BPA Alert

Genomic Medicine – GUARDD Study

POSITIVE RESULT:
This patient has INCREASED RISK for End Stage Kidney Failure according to *APOL1* genetic testing (result: G1/G1)

Evidence suggests that good blood pressure control and renal function testing may forestall kidney failure.

Recent blood pressure readings were:
12/15/2011 3/23/2012 6/1/2013
140/90 130/85 120/80

[Click here for provider information](#)

[Click here for patient materials](#)

Note: These results will be filed under Labs / Genetics.

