8. STATISTICAL ANALYSIS PLAN AND SAMPLE SIZE

8.1 Sample Size Determination

The study will randomize 2050 patients to either immediate or delayed genetic testing in a ratio of 7:1 respectively. We anticipate that of the 1800 patients who will be tested immediately approximately 250 will test positive. For this aim, we hypothesize that APOL1 positive patients will achieve 40% correct utilization of serum creatinine and/or urine albumin tests for “standard renal care” in patients with hypertension, compared to

30% for APOL1 negative patients. With an estimated 250 APOL1 positive and 1550 APOL1 negative we will have 87% power to detect the difference of interest using a two sided chi-square test.

Power calculations for this sub-aim are based on reduction of systolic blood pressure at three months after enrollment. For patients who test APOL1 positive we anticipate a 5 mmHg reduction in systolic blood pressure, compared to no change in patients who test APOL1 negative. Assuming that the standard deviation for differences in blood pressure between baseline and 3 month in both arms is 20 mmHg, a total of 250 patients testing positive and 1550 testing negative provides approximately 95% power to detect a difference of 5 mmHg in SBP between these two groups. If the standard deviation is larger than assumed, say 25 mmHg, power will still exceed 80%. Power is based on a 0.05 level two-tailed t-test of the difference in SBP at 3 months.

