8.2 General Statistical Methods

We will use mean and standard deviation to describe continuous variables, proportions for categorical variables; t-tests or analysis of variance (ANOVA) to compare continuous variables, and chi-square or Fisher's exact test to compare categorical variables by groups. To test significance of changes within groups over time, we will use paired t-tests for continuous and McNemar's tests for categorical variables. We will use linear mixed models to test the difference in SBP change over time between *APOL1* positives and negatives by entering the interaction term of time and *APOL1* status and adjusting for confounders, and generalized estimating equation methodology to test the change in controlled SBP status and renal function testing overtime between *APOL1* positives and negatives, and similarly between *APOL1* positives and controls.

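### Does the renal primary endpoint need a written counting window, and do its 30% and 40% rates need a stated time period?

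*Combined protocol and SAP*

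**What the plan says.** Section 2.1 sets both primary endpoints, renal test use and systolic blood pressure (SBP), as a comparison of positives with participants who are "APOL1* negative at three months after enrollment". Section 2.2 lists the 12-month reading of the primary outcomes as secondary.

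The planning text is less even. Section 3.4 ties the blood-pressure effect to a time, a "5mmHg improvement in systolic blood pressure at 3-month follow up". For the renal endpoint, section 8.1 supposes that "APOL1 positive patients will achieve 40% correct utilization of serum creatinine and/or urine albumin tests", against 30% in negatives, and names no period. With 250 positives and 1550 negatives it states 87% power for a two-sided chi-square test.

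Two sets of dates lie nearby. Section 6.3 says of study visits: "Follow-up visits will be completed between 14 days prior and one month after the projected follow-up date". Section 6.7 extracts EHR data for "12 months prior to randomization and 12 months after randomization for all enrolled participants". Section 8.2 plans generalized estimating equations "to test the change in controlled SBP status and renal function testing overtime" and names no baseline period.

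On exposure, section 6.6 allows about 1 to 4 weeks for results. Positives are scheduled for an in-person visit, while APOL1 "negative participants will have their tests results returned by phone". The provider alert fires only after the result has been returned, in the participant's "electronic health record the next time a primary care provider opens it".

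**The concern.** Blood pressure can be read on a day, but whether a test was ordered can only be judged over an interval, and that interval is not written out. If counting stopped at the 3-month visit, a later visit would give more time to record a test. The groups are unblinded and positives have an extra in-person contact, so visit timing could in principle differ by group and mimic an effect or hide one. Participants who miss the visit would have no end date.

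The planning rates raise a second doubt. If 30% and 40% were yearly figures, or if 40% held only for positives whose clinician had seen the alert, 87% would not be the power at three months. A wide extract with no written sub-window also seems to leave room to choose the window after the data are seen.

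**Working it through.** **1. The plan's own figure.** Inputs from section 8.1: 40% vs 30%, 250 vs 1550, two-sided chi-square. The 0.05 level is stated there only for blood pressure and is assumed here for the renal endpoint.

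- Pooled rate: (250 × 0.40 + 1550 × 0.30) / 1800 = 0.3139
- Null standard error: √[0.3139 × 0.6861 × (1/250 + 1/1550)] = 0.03163
- Alternative standard error: √[0.40 × 0.60/250 + 0.30 × 0.70/1550] = 0.03310
- Power: Φ[(0.10 − 1.96 × 0.03163) / 0.03310] = Φ(1.148) = 87.5%

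The stated 87% reproduces, and it uses all 250 positives at 40%, alerted or not.

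**2. Which window the text supports.**

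| Question | Where the plan answers it |
|---|---|
| Start | Enrollment (2.1). Randomisation takes place at the baseline visit (6.2), so the two coincide. |
| End | Three months (2.1). Twelve months is a separate secondary reading (2.2). |
| Source | EHR, anchored to randomisation, for all enrolled (6.7) |
| Visit window | Applies to study visits, which collect surveys, blood pressure and weight (6.3). No section links it to the renal count. |

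The 12-month look-back also holds an equal three-month period before randomisation, so a matching baseline for section 8.2 is available.

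**3. The visit-closed reading.** Assume steady ordering at 30% per three months (13.04 weeks), so p(w) = 1 − 0.7^(w/13.04). The visit window runs from 13.04 − 2 = 11.04 weeks to 17.39 weeks (four months).

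- p(11.04) = 26.1%; p(17.39) = 37.8%. The span is about 12 points.

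That span separates two individuals at opposite edges of the window. It would be a group difference only if every positive came on the last day and every negative on the first. With no true effect and negatives at 30%, a mean delay among positives gives:

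| Mean delay in positives | Positive rate | Two-sided rejection rate |
|---|---|---|
| 1 day | 30.3% | 5.1% |
| 3 days | 30.8% | 5.9% |
| 1 week | 31.9% | 9.6% |
| 2 weeks | 33.7% | 22.6% |

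With a true 40% and positives seen 1 or 2 weeks earlier, the positive rate is 37.6% or 35.1% and power is 67% or 37%. If 10% or 20% missed the visit and were lost (225 vs 1395, 200 vs 1240), power is 84.0% or 79.7%. All of these need a count that ends at the visit, and the shifts are assumed.

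**4. Yearly rates.** Steady ordering would give 1 − 0.7^0.25 = 8.5% and 1 − 0.6^0.25 = 12.0% at three months, and power of 43%. If all 10 points came in the first three months (8.5% vs 18.5%), power is 99%. The spread shows only that this assumption is unconstrained.

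**5. The effect confined to alerted positives.** If 90% or 80% are alerted and the rest stay at 30%, the positive average is 39% or 38% and power is 80% or 71%. Step 1 does not use this reading.

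**6. The price of a count that starts at randomisation.** Suppose instead that 40% were the rate under full exposure for 13.04 weeks, with the base rate until the result is reported after d weeks: p = 1 − 0.7^(d/13.04) × 0.6^((13.04 − d)/13.04).

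- d = 1: 39.3%, power 83%
- d = 4: 37.1%, power 61%

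A randomisation-anchored count is thus a trade-off. It treats both groups alike but includes time before the result is known.

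**The case for a change.** The strongest case is that a primary endpoint should be computable in only one way. Three months is a point and not an interval, the extract spans 24 months, and no section rules out closing the count at the visit. Section 6.6 foresees positive results that remain unreturned for three months or more, so some clinicians may be unalerted at the primary reading. A sentence of definition would cost nothing.

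The factual part stands: counting dates, a baseline period for change, and a period for 30% and 40% are not written. The inference to harm does not. Closing the count at the visit means borrowing a rule written for visits and applying it to clinician behaviour recorded elsewhere. Losing non-attenders would mean setting aside an extract that covers everyone enrolled. Late or missing alerts dilute the effect, but an average over all positives already contains that dilution. A comparison of 12 months before with 3 months after would indeed mislead, since 30% per three months is 1 − 0.7^4 = 76.0% per year, but no section plans it. In the comparison of positives with negatives, both groups would have the same windows.

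**Conclusion.** No change to the plan is needed. The counting window is unwritten but can be inferred: EHR-recorded tests in the three months after enrollment, for all enrolled participants, in the same dates for both groups. On that reading 87% is correct (87.5%), 40% is already the average over all 250 positives, and neither the sample size nor the data collection would move.

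The larger figures are arithmetically sound, but each depends on a premise absent from the documents: a visit-closed count, visit timing that differs by group, yearly rates, or a 40% limited to alerted positives. Nor does writing down a day 0 to 91 window bring a clear gain. If 40% were a full-exposure rate, the 1 to 4 week result delay would bring power to about 83% to 61%, so the choice of start date is a matter of judgement. The conclusion rests on the three-month reading of section 2.1 and a 0.05 level for the renal test. It does not address which tests count toward the endpoint, which sections 2.1, 3.4 and 8.1 word differently.
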